### 8.3.3.2 RELATIONSHIP TO STUDY INTERVENTION

The data monitoring and safety board physician will also classify the relationship of the AE to the study drug as follows:

- **Certain:** There is sufficient medical data supporting causality of the AE to the study drug. The AE resolves or improves with withdrawal of the study drug and, when possible, recurs with reintroduction of study drug
- **Probable:** There is sufficient medical data supporting causality of the AE to the study drug. The AE resolves or improves with withdrawal of the study drug. Reintroduction of the study drug is not required
- **Possible:** There is sufficient medical data supporting causality of the AE to the study drug. The resolution or improvement of the AE with study drug withdrawal is unclear or did not occur.
- **Unlikely:** There is insufficient medical data supporting the causality of the AE to the study drug, but a temporal relationship to study drug exposure is present.
- **No relationship:** There is no temporal relationship between study drug exposure and the AE.

---

### 8.3.4 TIME PERIOD AND FREQUENCY FOR EVENT ASSESSMENT AND FOLLOW-UP

The occurrence of an adverse event (AE) or serious adverse event (SAE) may come to the attention of study personnel during study visits and interviews of a study participant presenting for medical care, or upon review by a study monitor.

All AEs including local and systemic reactions not meeting the criteria for SAEs will be captured on the appropriate case report form (CRF). Information to be collected includes event description, time of onset, clinician's assessment of severity, relationship to study product (assessed only by those with the training and authority to make a diagnosis), and time of resolution/stabilization of the event. All AEs occurring while on study will be documented appropriately regardless of relationship. All AEs will be followed to adequate resolution.

Any medical condition that is present at the time that the participant is screened will be considered as baseline and not reported as an AE. However, if the study participant's condition deteriorates at any time during the study, it will be recorded as an AE.

Changes in the severity of an AE will be documented to allow an assessment of the duration of the event at each level of severity to be performed. AEs characterized as intermittent require documentation of onset and duration of each episode.

Study coordinator will record all reportable events with start dates occurring any time after informed consent is obtained until 7 (for non-serious AEs) or 30 days (for SAEs) after the last day of study participation. At each study visit, the investigator will inquire about the occurrence of AE/SAEs since the last visit. Events will be followed for outcome information until resolution or stabilization.

---

### 8.3.5 NON-SERIOUS ADVERSE EVENT REPORTING

The collection of non-serious AE information should begin at initiation of study drug. All non-serious adverse events (not only those deemed to be treatment-related) should be collected continuously during the treatment period and for a minimum of 30 days following the last dose of study treatment. Non-serious AEs should be followed to resolution or stabilization, or reported as SAEs if they become serious. Follow-up is also required for non-serious AEs that cause interruption or discontinuation of study drug and for those present at the end of study treatment as appropriate.

Nonserious Adverse events will be reported to the Data Safety and Monitoring Board every 3 months.

Nonserious Adverse Events are provided to BMS via annual safety reports (if applicable), and interim or final study reports.

---

### 8.3.6 SERIOUS ADVERSE EVENT REPORTING

Following the subject's written consent to participate in the study, all SAEs, whether or not related to the BMS product under study, must be collected, including those thought to be associated with protocol-specified procedures. SAEs must be recorded on FDA MedWatch 3500A Form and reported to BMS (or designee) within 24 hours/1 business day to comply with regulatory requirements. A form should be completed for any event where doubt exists regarding its status of seriousness. Although overdose and cancer are not always serious by regulatory definition, these events should be recorded on a form and reported to BMS within 24 hours/1 business day.

All SAEs must be reported by confirmed facsimile (fax) transmission or reported via electronic mail to:  
**SAE Email Address:** [contact]  
**SAE [contact]

If only limited information is initially available, follow-up reports may be required.

For studies capturing SAEs through electronic data capture (EDC), electronic submission is the required method for reporting. The paper forms should be used and submitted immediately, only in the event the electronic system is unavailable for transmission. When paper forms are used, the original paper forms are to remain on site.

If it is discovered a patient is pregnant or may have been pregnant at the time of exposure to the BMS product under study, the pregnancy, AEs associated with maternal exposure and pregnancy outcomes must be recorded on a Pregnancy Surveillance Form and reported to BMS (or designee) within **24 hours/1 business day** by confirmed fax or reported via electronic mail to [contact]. If only limited information is initially available, follow-up reports may be required. The original BMS forms are to remain on site. Follow-up information should be obtained on pregnancy outcomes for one year following the birth of the offspring.

Any pregnancy that occurs in a female partner of a male study participant should be reported to BMS. Information on this pregnancy will be collected on the Pregnancy Surveillance Form.

---

### 8.3.7 NONSERIOUS ADVERSE EVENT REPORTING

The collection of non-serious AE information should begin at initiation of study drug. All nonserious adverse events (not only those deemed to be treatment-related) should be collected continuously during the treatment period and for a minimum of 30 days following the last dose of study treatment.

Nonserious AEs should be followed to resolution or stabilization, or reported as SAEs if they become serious. Follow-up is also required for non-serious AEs that cause interruption or discontinuation of study drug and for those present at the end of study treatment as appropriate.

Nonserious Adverse Events are provided to BMS via annual safety reports (if applicable), and interim or final study reports.

---

#### 8.3.8 SAE RECONCILIATION

The investigator will reconcile the clinical database SAE cases transmitted to BMS Global Pharmacovigilance (GPV&E). Frequency of reconciliation will be done every three months and once prior to study database lock. BMS GPV&E will e-mail upon request from the investigator, the GPV&E reconciliation report. Requests for reconciliation should be sent to [[contact]](mailto:[contact]). The data elements listed on the GPV&E reconciliation report will be used for case identification purposes. If the investigator determines a case was not transmitted to BMS GPV&E, the case will be sent immediately.

---

#### 8.3.9 LABORATORY TEST ABNORMALITIES

All laboratory test results captured as part of the study should be recorded following institutional procedures. Test results that constitute SAEs should be documented and reported to BMS as such.

The following laboratory abnormalities should be documented and reported appropriately:

- any laboratory test result that is clinically significant or meets the definition of an SAE
- any laboratory abnormality that required the participant to have study drug discontinued or interrupted
- any laboratory abnormality that required the subject to receive specific corrective therapy.

It is expected that wherever possible, the clinical rather than laboratory term would be used by the reporting investigator (eg, anemia versus low hemoglobin value).

---

#### 8.3.10 OTHER SAFETY CONSIDERATIONS

Any significant worsening noted during interim or final physical examinations, electrocardiograms, X-rays, and any other potential safety assessments, whether or not these procedures are required by the protocol, should also be recorded as a non-serious or serious AE, as appropriate, and reported accordingly.

---

#### 8.3.11 REPORTING EVENTS TO PARTICIPANTS

Study participants will be informed of any adverse events or incidental findings through a letter or phone call. In the case of a serious adverse event, the participant will be informed through a phone call within 48 hours of the occurrence. If patient is not reachable, attempts will be made to reach the alternative contact person and the primary treating physician, whose contact information will be sought from the subject at enrollment. The participant will be encouraged to seek care with the primary

treating physician to treat SAEs and to assess any incidental findings, such as findings on brain imaging that require further assessment.

Interpretation of the brain MRI will be performed by a board certified clinical Radiologist and a report generated in the patient's clinical record. This report will be shared with the participant through a letter. This report is however different from the more detailed analysis of the sequences that will be performed by the study Radiologist in a blinded fashion. The results of the cognitive function testing will be shared with individual participants only in the event of diagnosis of dementia, which is expected to have an impact on the overall management of the subject. The aggregate results of the study will be shared with all the participants once published in a peer review journal.

## 8.4 UNANTICIPATED PROBLEMS

### 8.4.1 DEFINITION OF UNANTICIPATED PROBLEMS (UP)

An UPIRTSO: An Unanticipated Problem Involving Risk to Subjects or Others is defined as any problem or event which, in the opinion of the Investigator, meets all three of the following criteria:

1. Serious: Serious problems or events that result in significant harm, (which may be physical, psychological, financial, social, economic, or legal) or places subjects or others at a greater risk of harm than was previously known or recognized. Note that actual harm need not have occurred for there to be a change in the risk/benefit ratio.

2. Unanticipated: A problem or event is "unanticipated" when it was unforeseeable at the time of its occurrence and is:

Not already described as a potential risk in the approved informed consent

Not already described as a potential risk in the approved protocol

Not listed in the Investigator's Brochure

Not part of an underlying disease

Occurred at an increased frequency or at an increased severity than expected

3. Related: A problem or event is "related" if it is possibly related to the research procedures.

### 8.4.2 UNANTICIPATED PROBLEM REPORTING

The Investigator must report a UPIRTSO to the IRB, using the IRB electronic Reportable Event form, within five working days of becoming aware of the problem or event. The report will include a detailed description of the event, incident, experience, or outcome.

All reportable events submitted to the IRB and meeting the UPIRTSO criteria will be sent to an IRB Chairperson for review. If the IRB Chairperson considers the event is a UPIRTSO, a convened IRB reviews it and determines whether it is a UPIRTSO or not. The investigator is notified in writing and the review, determination, and investigator communication is documented in the IRB electronic system.

A UPIRTSO, as determined by the convened IRB, is reported to the Mayo Clinic Institutional Official and other relevant Federal agencies, when required, within 30 days from the date of IRB determination. The investigator is notified in writing of this action.

The investigator will submit a modification application to the IRB if the problem or event requires revision of the protocol and/or consent document.

If the convened IRB confirms the UPIRTSO, the investigator reports the IRB's determination to the research project sponsor.

### 8.4.3 REPORTING UNANTICIPATED PROBLEMS TO PARTICIPANTS

Unanticipated problems occurring in individual subjects will be reported to the subject using the methods described for AEs and SAEs noted above.

## 9 STATISTICAL CONSIDERATIONS

### 9.1 STATISTICAL HYPOTHESES

- Primary Efficacy Endpoint:

Treatment with Apixaban is associated with reduced rate of decline in global cognitive function score compared to treatment with Warfarin in AF patients  $\geq 60$  years of age and CHA2DS2-VaSC score  $\geq 2$ .

#### ***Measurement of primary endpoint: The individual cognitive domain and global cognitive function score***

All enrolled subjects will undergo assessment of cognitive function at (1) enrollment, (2) 1 year and (3) 2 years.

AF may have a greater impact on non-memory cognitive domains such as executive function, thus predisposing to non-amnesic dementia. Hence we will test individual cognitive domains to increase the sensitivity of the tests.

The following standardized tests will be administered at each visit by a trained neuropsychometrist.

#### Testing of four major cognitive function domains

5. Executive function - Trail Making Test B and Digit Symbol Substitution Test
6. Language - Boston Naming Test and Category Fluency
7. Memory - Logical Memory-II (delayed recall), Visual Reproduction-II (delayed recall) and Auditory Verbal Learning Test (delayed recall)
8. Visuospatial - Picture Completion and Block Design

Questionnaires to rule out competing diagnoses:

1. The Beck Depression Inventory
2. The Beck Anxiety Inventory

An informant, identified by the subject as someone with whom they have contact at least once every week, will be interviewed in person or by telephone to complete the following:

1. Clinical dementia rating scale (CDR)
2. Functional assessment questionnaire

For patients lost to clinic follow-up, assessment of cognitive state will be performed using the following questionnaires administered over the telephone:

Telephone interview of cognitive status (TICS-M) (administered to subject)

2. Clinical dementia rating scale (administered to informant)
3. Functional assessment questionnaire (administered to informant)

Patients who no longer present for in person neurocognitive assessment will be censored from the analysis of the primary endpoint of neurocognitive function scores. The telephone interview will be used to classify as MCI / dementia and the data will be used for this secondary endpoint only.

#### *Adjustment of Neurocognitive function scores using normative data and derivation of 'Global cognitive function score'*

The raw scores on each neuropsychological test will be transformed into age- and education-adjusted scores using Mayo's Older American Normative Studies normative data. The adjusted scores within each of the 4 domains will be added to obtain the domain specific score. Since different numbers of tests are used within each domain (i.e., 2 tests for the executive, language, and visuospatial domains versus 3 tests for memory), the domain scores will also be scaled for the number of tests to allow comparisons across domains. The global cognitive function score will then be derived using an average of the 4 domain specific scores.

The performance of a person in a particular domain and their global performance will then be measured by comparing the person's score with the score in a normal person that has been previously established to derive a 'z-score'. These comparisons rely on extensive previous normative work we have performed in assessing the cognitive abilities of the population from which the sample will be derived. The tests and definitions provided here have been previously described in detail by our group. The tests will parallel those used by the NIH funded Mayo Clinic Study of Aging, a large ongoing community based study of cognitive function in Olmsted County, MN.

The 'z-score' in individual cognitive domains and the global cognitive function score will be plotted at each time point for the two treatment groups to assess temporal changes.

- Secondary Efficacy Endpoints:

Treatment with Apixaban is associated with lower rate of development of new dementia or mild cognitive impairment compared to treatment with warfarin.

#### ***Measurement of secondary endpoint: Mild cognitive impairment or dementia***

The CDR score (range 0–3) will be assessed in addition to the results of the neuropsychological testing. A team of Neurologist and Neuropsychometrist will assign a diagnosis of normal cognition or mild cognitive impairment or dementia to each subject at each time point. This team will be blinded to treatment assignments. Each assessment of an individual patient will be assessed independent of prior assessments. The definitions used are as follows:

#### *Dementia*

Subjects with a CDR 1 will be classified as demented if they meet DSM-V criteria for ‘major neurocognitive disorder’ as follows:

1. Evidence of significant cognitive decline from a previous level of performance in one or more cognitive domains based on:
  - a. Concern of the individual, a knowledgeable informant, or the clinician that there has been a significant decline in cognitive function; and
  - b. A substantial impairment in cognitive performance, preferably documented by standardized neuropsychological testing.
2. The cognitive deficits interfere with independence in everyday activities.
3. The cognitive deficits do not occur exclusively in the context of delirium and are not better explained by another mental disorder.

For subjects with CDR 0.5, a committee of the examining neuropsychologist and physician will critically examine the available tests to determine whether the DSM-V criteria for dementia or MCI are met.

#### *Mild cognitive impairment*

The criteria for diagnosis of MCI are: cognitive concern expressed by a physician, informant, participant or nurse; cognitive impairment in 1 or more domains; normal functional activities and not demented. Subjects with MCI can have a CDR of 0 or 0.5; however, the final diagnosis of MCI will not be based exclusively on the CDR but rather on all available data. A committee of the examining neuropsychologist and physician will critically examine the available tests to determine whether the criteria for MCI are met.

#### *Normal Cognition*

Subjects judged to have no cognitive impairment based on the criteria above and received a CDR of 0, will be considered as cognitively normal.

Treatment with Apixaban is associated with lower incidence of new cerebral infarction and cerebral microbleeds noted on brain MRI imaging.

Measurement of secondary endpoint: This will be performed using brain MRI as noted above.

## 9.2 SAMPLE SIZE DETERMINATION

Sample size calculation is based on the primary endpoint, the rate of decline in the global cognitive function score. The sample size calculations are based on data from the Mayo Clinic Study of Aging which has enrolled community dwelling individuals to perform the same battery of neurocognitive tests proposed in this study. We investigated the rate of decline in the global cognitive function score in (1) patients with and without AF and (2) in AF patients on warfarin vs. not on warfarin. The Mayo Clinic Study of Aging (MCSA) has identified a significant decline in the individual and global cognitive function scores in patients with AF compared to those without AF. In addition, the rate of decline was similar in AF patients treated with warfarin and those not treated with warfarin. The observed rate of decline in global cognitive score in AF patients on warfarin was -0.12 / year (SD 0.16). A reduction in the rate of decline in the global cognition function score of 0.05/year with Apixaban compared to Warfarin was considered clinically relevant. We used R to calculate power as a single sided test of superiority of Apixaban over Warfarin. A sample size of 140 in each arm is required to achieve >80% power to detect

the difference stated assuming an alpha error of 0.05. Assuming a screen failure rate of 20%, a total of 175 will be accrued in each arm.

Enrollment will be age and gender stratified with goal of enrolling >50% patients over the age of 70 years in whom the risk of cognitive decline is greater. Recruitment of the required number of subjects will be feasible given the high volume of AF patients in the local community and those seeking care for AF at the Mayo Clinic. For example, 5000 individuals developed incident (new onset) AF in Olmsted county alone after the year 2000. The rate of prevalent AF is higher in this population. The other 7 counties from which participants will be recruited have similar population demographics and prevalence of AF. We anticipate that we will be able to recruit the required number of subjects in the first year of the study.

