### 3 OBJECTIVES AND ENDPOINTS

OBJECTIVES	ENDPOINTS	JUSTIFICATION FOR ENDPOINTS
Primary		

To assess the change in global cognitive function using standardized neurocognitive assessment in patients with atrial fibrillation over the age of 60 years with CHA2DS2-VASc score <math>\geq 2</math> treated with Apixaban versus warfarin
	
The individual cognitive domain and global cognitive function score using a battery of standardized neurocognitive function tests (presented below in detail).
 
 
○ All enrolled subjects will undergo assessment of cognitive function at (1) before or within 1 month of randomization (2) 1 year and (3) 2 years.
 
	
Cognitive function scores are chosen as the primary end point due to their sensitivity to detect changes in cognitive function within a short span of time. While dementia is also an important end point, it is increasingly recognized that milder degrees of cognitive dysfunction are more prevalent and may have an important impact on a person’s quality of life and morbidity. Early recognition of cognitive decline can lead to earlier intervention to either treat or prevent progression. Hence the primary end point of decline in cognitive function in one or more domains will be a clinically relevant and a patient centered outcome.
 
Additionally, AF may have a greater impact on non-memory cognitive domains such as executive function, thus predisposing to non-amnesic dementia. Hence we will test individual cognitive domains to

OBJECTIVES	ENDPOINTS	JUSTIFICATION FOR ENDPOINTS
		increase the sensitivity of the tests.
Secondary		

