### **5.2 EXCLUSION CRITERIA**

An individual who meets any of the following criteria will be excluded from participation in this study:

1. Patients who are not a candidate for oral anticoagulation as assessed by a treating physician including the presence of active bleeding.
2. Prior treatment with Apixaban for >1 month. (Prior exposure to warfarin or novel direct oral anticoagulants other than Apixaban is not an exclusion criterion).
3. Known hypersensitivity to warfarin or Apixaban.
4. CHA2DS2-VASc score <2

5. Valvular AF defined as history of rheumatic valve disease, moderate or greater mitral stenosis, and presence of a mechanical cardiac valve.
6. Need for dual anti-platelet therapy with aspirin and another agent such as a thienopyridine.
7. Aspirin monotherapy with doses > 100 mg if the patient is unable to reduce the dose to <100 mg.
8. Severe renal insufficiency (serum creatinine level of >2.5 mg/dl or calculated creatinine clearance of <25 ml/minute) or dialysis.
9. Prior severe bleeding including intracranial hemorrhage and GI bleed requiring transfusion.
10. Recent stroke (within 7 d)
11. Known diagnosis of dementia or dementia diagnosed at first evaluation.
12. Presence of MRI non-compatible implanted devices including cardiac implantable electronic devices. Patients with MRI conditioned cardiac implantable electronic devices will also be excluded. This is done in light of concerns regarding patient safety in MRI scanner.
13. Inability to undergo MRI due to claustrophobia.
14. Current or expected systemic treatment with strong dual inducers of CYP3A4 and P-gp (e.g., rifampin, carbamazepine, phenytoin, St. John's wort) because such drugs will decrease exposure to apixaban
15. Current or expected systemic treatment with strong dual inhibitors of CYP3A4 and P-glycoprotein (e.g., ketoconazole, itraconazole, ritonavir, or clarithromycin) in patients who would qualify for Apixaban dose of 2.5 mg BID.
16. Currently enrolled in another investigational device or drug trial that has not completed the primary endpoint or that clinically interferes with the current study endpoints.
17. Co-morbid condition(s) that could limit the subject's ability to participate in the trial or to comply with follow-up requirements, or that could impact the scientific integrity of the trial.

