### 5.4 SCREEN FAILURES

Screen failures are defined as participants who consent to participate in the clinical trial but are not subsequently randomly assigned to the study intervention or entered in the study. An example of a screen failure is someone who is diagnosed with newly recognized dementia or intracerebral hemorrhage following the administration of the baseline neurocognitive assessment and brain MRI. Information on screen failures will be collected for purposes of reporting as follows: demography, eligibility criteria, reason for screen failure and any serious adverse event.

Individuals who do not meet the criteria for participation in this trial (screen failure) will not be rescreened.

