## 5.5 STRATEGIES FOR RECRUITMENT AND RETENTION

1. This is a single center study that will be conducted at the Mayo Clinic, Rochester, MN. Target study sample is total of 280 patients. Assuming a screen failure rate of 20%, target accrual is 350 participants. Accrual will be completed in 1 year. The last patient will complete follow-up 2 years later.
2. In order to enrich the study for the population at risk of the primary end point, at least 50% of the enrollees will be >70 y of age.
3. Participants will be identified using two strategies: (1) Individuals with AF living in the 8 counties of Southeast Minnesota (Dodge, Fillmore, Goodhue, Houston, Olmsted, Mower, Wabasha and Winona counties) will be screened for eligibility. Such patients will be identified using the record linkage system of the Rochester Epidemiology Project and Mayo Clinic, Rochester clinical records. Potential participants with AF diagnosed in Olmsted county have already been identified through prior work the investigators have done. (2) Individuals seen in the inpatient and outpatient clinics at Mayo Clinic, Rochester, MN with a diagnosis of AF will also be screened for eligibility. Such patients will be identified by the treating physician, using screening of their medical records and through the Mayo ECG laboratory which flags patients with new identification of AF.
4. Potential participants will be approached using one or more of the following: (1) direct patient contact in the clinic or hospital, (2) through letters and (3) phone calls.
5. The ECG documentation of AF will be confirmed using review of the medical records. Eligibility for the study will be determined first using medical records and confirmed by direct interview of the patient prior to enrollment.
6. Participants will be compensated for their participation in the study as follows: (1) each participant will be given \$15 at the time of each neurocognitive assessment and (2) a Mayo parking voucher at the time of each MRI assessment. The compensation is intended to encourage patients to continue study related tests by providing partial compensation for travel expenses.

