## 8 STUDY ASSESSMENTS AND PROCEDURES

### 8.1 EFFICACY ASSESSMENTS

#### **Screening assessment**

Screening for eligible participants will be performed using the Mayo medical records by a study coordinator. Only patients who have previously given consent to the use of their medical records for research purposes will be screened. ECG, Holter, telemetry recordings will be reviewed to confirm the diagnosis of AF. Charts will be reviewed to assess eligibility for the study including past medical history, current medications, laboratory tests and calculation of the CHA2DS2-VaSC score. The creatinine will be checked if a measurement within 3 months of enrollment is not available.

Potential participants will be contacted in person or through a letter or on the phone. Interested persons will be interviewed on the phone to confirm eligibility and will have a blood test for creatinine if needed. Once enrolled, subjects will be randomized to one of the study arms and will start study drug.

Baseline assessment of brain MRI will be performed prior to initiation of study drug. Baseline assessment of cognitive function will be performed prior to or within 1 month of enrollment. Subsequent assessments will be performed at 1 and 2 year follow-up or within a 3 month time frame of this date.

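### Does the >80% power claim in section 9.2 fail because nothing is allowed for loss after randomisation?

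*Combined protocol and SAP*

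**What the plan says.** Section 9.2 powers the trial on the rate of decline in the global cognitive score. It takes SD 0.16 per year from warfarin-treated AF patients in a community cohort, a difference of 0.05 per year, and a one-sided test at 0.05. It concludes: "A sample size of 140 in each arm is required to achieve >80% power to detect" that difference. It then adds: "Assuming a screen failure rate of 20%, a total of 175 will be accrued in each arm". Section 5.5 has the same inflation in total numbers, with a target sample of 280: "Assuming a screen failure rate of 20%, target accrual is 350 participants".

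Section 5.4 defines the group that this allowance covers, which also takes in people who never enter the trial: "Screen failures are defined as participants who consent to participate in the clinical trial but are not subsequently randomly assigned to the study intervention".

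Loss after randomisation is dealt with elsewhere, without a rate:
- **Section 7.1:** participants who change anticoagulant are withdrawn and censored. An exit assessment is done if more than 6 months have passed since the last one; otherwise the last assessment is used. Stopping the anticoagulant does not by itself end participation.
- **Section 7.2:** only people randomised but never treated may be replaced.
- **Section 9.1:** people who no longer attend in-person testing are censored from the primary endpoint.
- **Section 9.4.1:** the primary analysis is a linear mixed effects model of the longitudinal scores.

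**The concern.** An allowance for screen failures protects the number randomised, not the number analysed. Here it brings 350 consenting people down to 280 randomised and stops there. This is a two-year, open-label trial in people aged 60 or over, at least half of them meant to be over 70, and a change of anticoagulant leads to withdrawal. Some loss is to be expected. If it is large enough, the real power is below the figure the trial was justified on.

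The number randomised also looks unsettled. Section 9.2 speaks of 175 accrued in each arm, and nobody has an arm before randomisation. Section 8.1 says "Once enrolled, subjects will be randomized to one of the study arms and will start study drug" and also "Baseline assessment of cognitive function will be performed prior to or within 1 month of enrollment"; section 3 allows the first cognitive test "before or within 1 month of randomization". Section 5.2 excludes "Known diagnosis of dementia or dementia diagnosed at first evaluation". Some people counted as screen failures could therefore be found after randomisation, which raises the question whether 140 or 175 per arm are randomised.

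**Working it through.** **Inputs from section 9.2.** Difference 0.05/year; SD 0.16, taken as equal in both arms; one-sided alpha 0.05; 140 per arm. Allocation is 1:1 (section 6.1.1).

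**1. The plan's own figure.** Standardised difference = 0.05 / 0.16 = 0.3125. For a two-sample t test the noncentrality is 0.3125 × √(n/2). At n = 140 this is 0.3125 × √70 = 2.61, and power is 83.2% (83.4% by the normal approximation). The claim of more than 80% reproduces.

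**2. The margin.** At 128 per arm power is 80.2%; at 127 it is 79.9%. The slack is 140 − 128 = 12 per arm, or 12/140 = 8.6%.

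**3. Worst case: lost participants contribute nothing.** The documents give no loss rate, so the rates are assumptions.

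| Loss | n per arm | Power |
|---|---|---|
| 0% | 140 | 83.2% |
| 5% | 133 | 81.5% |
| 10% | 126 | 79.6% |
| 15% | 119 | 77.6% |
| 20% | 112 | 75.4% |

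**4. Closer to the planned analysis.** A mixed model uses every score obtained, and section 7.1 adds an exit score for many who leave. To illustrate, suppose that 0.16 is the SD of a slope fitted to visits at 0, 1 and 2 years, and that the true slopes have SD s between 0.08 and 0.13. Neither assumption is in the documents.
- The squared visit times about their mean sum to 2, so 0.16² = s² + (residual variance)/2, and residual variance = 2 × (0.16² − s²). This is 0.0384 at s = 0.08 and 0.0174 at s = 0.13.
- Let withdrawal fall evenly over two years, with an exit score only if more than 6 months have passed since the last test. Averaged over withdrawal times, a person who leaves carries a fraction f = 0.328 (s = 0.08) to 0.432 (s = 0.13) of the slope information of a completer.
- Effective n = 140 × (1 − L × (1 − f)), where L is the proportion lost.

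| Loss L | Effective n per arm | Power |
|---|---|---|
| 10% | 130.6 to 132.1 | 80.9% to 81.3% |
| 15% | 125.9 to 128.1 | 79.6% to 80.2% |
| 20% | 121.2 to 124.1 | 78.3% to 79.1% |

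The loss at which power reaches 80% becomes 0.0857 / (1 − f), that is 0.0857/0.672 = 12.8% to 0.0857/0.568 = 15.1%. It is higher if losses come mostly late.

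**5. How many are randomised.** 350 × 0.8 = 280 and 175 × 0.8 = 140. Section 5.5 calls 280 the study sample and 350 the accrual, and section 5.4 places screen failures before randomisation or entry. Section 5.4 even gives dementia newly found at the baseline assessment as an example of a screen failure. Read together, these sections mean 350 consented and 280 randomised, 140 per arm. The phrase in section 9.2 attaches the consented number to arms, which is a slip of wording. If 175 per arm were randomised and the 20% then failed screening, 140 would again remain, so this reading does not create an attrition margin.

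**The case for a change.** The best case for acting is that zero loss is not a credible silent assumption in this population, and that the protocol itself produces loss by withdrawing people who change anticoagulant and censoring those who stop attending. The mixed model does not rescue everyone. A person with only a baseline score says essentially nothing about slope, and section 7.1 waives the exit test within 6 months of the last one, so the earliest leavers have no second score. Section 9.1 could also be read strictly, as removing a person's scores altogether, which would bring the worst-case table into play. One or two sentences would settle the matter.

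Much of this stands. The omission is real, and a fuller section 9.2 would give an expected loss and the power after it. But the threshold of about 9% needs every lost participant's later scores to be absent or discarded. Section 7.1 says that the last assessment will be used, and section 9.4.1 plans a model that can use incomplete series. The plan also works to limit loss: study procedures continue after the drug is stopped (7.1), missed visits are chased (7.3), and testing visits are compensated (5.5).

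The timing of baseline cognitive testing is a genuine tension between sections 3, 5.2, 5.4 and 8.1. It concerns when eligibility is confirmed and is separate from the power calculation.

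**Conclusion.** No change follows. The power statement is right for the inputs it gives, 83.2% at 140 per arm with complete data, and nothing in the documents shows that it is missed. What is absent is a stated loss rate. Under the planned analysis the likely effect is small: power stays at about 81% with 10% loss and is 78% to 79% with 20%, at most about 2 points under the target. In the worst case, with nothing contributed, the shortfall at 20% loss is 80 − 75.4 = 4.6 points.

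These sizes rest on SD 0.16 applying to two-year slopes in this trial and on assumed loss rates. The milder figures also rest on an assumed true-slope SD of 0.08 to 0.13 and evenly spread withdrawals; they illustrate the effect and do not bound it.

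Writing down an expected loss would leave the number randomised, the visits, the model and the reading of the result as they are. The wording about 175 in each arm is a clerical slip that sections 5.4 and 5.5 resolve to 280 randomised.
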